6.4.5.2. Independent Data Monitoring Committee

In order to ensure the safety of the subjects during the entire study period, an Independent Data Monitoring Committee (IDMC) **has been** appointed to monitor the safety and tolerability of the vaccine/placebo administered in the trial and, if necessary, make recommendations to the sponsor concerning the modification or termination of the trial. The IDMC will perform safety reviews twice a year or more frequently if deemed necessary on an ongoing basis during the study period. **(Amended: 29 January 2014)**

An independent statistical team (i.e., comprising members who are neither GSK employees neither Aeras employees and who are not involved in the study management) will be appointed by GSK Biologicals. This team will be unblinded to treatment assignment and provide all necessary tables, listings, figures and individual subject data to the IDMC.

The IDMC consists of clinical experts who are not involved in the conduct of the study and an independent statistician. The role of the IDMC will be to review the progress of the trial and safety assessments to detect evidence of safety issues for the subjects from the time of first vaccination and throughout the duration of the trial. A report, with recommendations as necessary, will be provided to the sponsor following each IDMC meeting. The frequency of IDMC sessions and other operational details are described in the IDMC charter. In case of a serious safety issue during the study, the sponsor will inform the IDMC as well as fulfil its regulatory obligation expeditiously. **(Amended: 29 January 2014)**

If during the course of enrolment and vaccination two or more related grade 2 or 3 respiratory AE are observed an ad hoc IDMC will be convened. (Amended: 29 January 2014)

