6.4.5.4. Rules for vaccination (Amended: 29 January 2014)**At individual subject level**

- *No second dose should be administered in a given subject who experiences Grade 3 redness and swelling, i.e. $\geq 100\text{mm}$, post dose 1 or Grade 2 or 3 respiratory AE post dose 1.*
- *No second dose should be administered in a given subject who develops TB disease after dose 1.*

At study level

- *An ad hoc IDMC review will be called if 2 or more subjects experience related Grade 2 or higher respiratory AEs within 90 days after any dose.*
- *Further enrolment and vaccination will be suspended if within 90 days after any study vaccine dose any of the following events are observed:*
 - *Related respiratory AE with Fatal outcome*
 - *Two or more subjects experiencing Grade 3 related Respiratory AE*
- *An ad hoc IDMC meeting will be called urgently for review. Vaccination may only be allowed to resume pending final VSMB approval.*

Table 6 Safety holding rules for vaccination (Amended: 29 January 2014)

Event	Grade	Occurrences	Action for subject(s)	Trial actions
Redness/Swelling at injection site (within 30 days after dose 1)	Grade 3 (>100mm)	any subject(s)	No dose 2 in same subject(s), keep in efficacy follow-up	-
TB disease (after dose 1)	n/a	Any subject(s)	No dose 2 in same subject(s), keep in efficacy follow-up	-
Respiratory SOC AE (within 90 days after dose 1)	Grade ≥ 2	1 subject	No dose 2 in same subject(s), but keep in efficacy follow-up	-
Respiratory SOC AE (within 90 days after dose 1)	Grade ≥ 2 related	≥ 2 subjects	Clinical assessment & further investigation at investigator discretion	Ad hoc IDMC review
Respiratory SOC SAE	Related & Fatal	≥ 1 subject		
Respiratory SOC AE (within 90 days after dose 1)	Grade ≥ 3, related	≥ 2 subjects	No dose 2 in same subject(s) Clinical assessment & further investigation at investigator discretion	Study Hold, IMDC Review, VSMB

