6.5. Outline of study procedures

Table 7 List of study procedures (Amended: 29 January 2014)

	Visit 1 Screening visit	Visit 2	Visit 3 ¹	Visit 4	Visit 5 ¹	Visit 6	Contact 1, 2, 3 and 4	Visit 7	Contact 5, 6, 7, 8, 9	Visit 8	Contact 10, 11, 12, 13, 14	Visit 9
Time point(s)	D-30 to D0	D 0	D 7	D 30	D 37	M 2	M 4, 6, 8, 10	M 12	M 14, 16, 18, 20, 22	M 24	M 26, 28, 30, 32, 34	M 36
Sampling Time point(s)	Pre V	Pre V	Post V1	Post V1	Post V2	Post V2	Post V2	Post V2	Post V2	Post V2	Post V2	Post V2
Dose		1		2								
All subjects												
Informed consent	•											
Check inclusion/exclusion criteria	•	•										
Collect demographic data	•											
Medical history	•	•										
Physical examination		•										
History-directed physical examination		0	0	0	0	0						
Resting vital signs		0		0								
HIV testing ² (up to ~ 2.5 mL/test)	•										•	
Record weight ³		•						•		•		•
Documentation of history of BCG vaccination/presence of scar	•										Visit 1	
Documentation of history of TB household contacts	•											
Pregnancy test (β-HCG urine)	•	•		•								
Study group and treatment number allocation for first dose		0										
Treatment number allocation for second dose				0								

CONFIDENTIAL

115616 (TUBERCULOSIS-018)
Protocol Amendment 5 Final

	Visit 1 Screening visit	Visit 2	Visit 3 ¹	Visit 4	Visit 5 ¹	Visit 6	Contact 1, 2, 3 and 4	Visit 7	Contact 5, 6, 7, 8, 9	Visit 8	Contact 10, 11, 12, 13, 14	Visit 9
Time point(s)	D-30 to D0	D 0	D 7	D 30	D 37	M 2	M 4, 6, 8, 10	M 12	M 14, 16, 18, 20, 22	M 24	M 26, 28, 30, 32, 34	M 36
Sampling Time point(s)	Pre V	Pre V	Post V1	Post V1	Post V2	Post V2	Post V2	Post V2	Post V2	Post V2	Post V2	Post V2
Dose		1		2								
Vaccination		●		●								
Recording of administered treatment number		●		●								
Check contraindications to subsequent vaccination		●		●								
Recording concomitant medication/vaccination		●	●	●	●	●	●	●	●	●	●	●
Recording intercurrent medical condition		●	●	●	●	●	●	●	●	●	●	●
Distribution of diary cards		0		0								
Return of diary cards				0		0						
Recording of unsolicited AEs and large swelling reactions		●	●	●	●	●						
Pre-vaccination assessment (including temperature)		●		●								
Blood sampling for QFTG (~ 3 mL)	●											
Sputum collection for Xpert testing	●											
Reporting SAEs	● ⁴	●	●	●	●	●	● ⁵	● ⁴	● ⁴	● ⁴	● ⁴	● ⁴
Reporting pIMDs	●	●	●	●	●	●	● ⁶					
Reporting pregnancy	●	●	●	●	●	●	● ⁶					
Diagnostic procedures for suspected pulmonary TB ⁷			●	●	●	●	●	●	●	●	●	●

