In case an emergency mass vaccination for an unforeseen public health threat (e.g.: a pandemic) is organised by the public health authorities, outside the routine immunisation program, the time period described above can be reduced if necessary for that vaccine provided it is licensed and used according to its SPC or PI and according to the local governmental recommendations and provided a written approval of the Sponsor is obtained.

- Immunoglobulins and/or any blood products administered during the study period.

7.7. Intercurrent medical conditions that may lead to elimination of a subject from ATP analyses

At each study visit subsequent to the first vaccination visit, it must be verified if the subject has experienced or is experiencing any intercurrent medical condition. If it is the case, the condition(s) must be recorded in the eCRF.

Subjects may be eliminated from the ATP cohort for immunogenicity if, during the study, they incur tuberculosis disease or any other condition that has the capability of altering their immune response or are confirmed to have an alteration of their initial immune status.

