While pregnancy itself is not considered an AE or SAE, any adverse pregnancy outcome or complication or elective termination of a pregnancy for medical reasons will be recorded and reported as an AE or a SAE.

Note: The pregnancy itself should always be recorded on an electronic pregnancy report.

The following should always be considered as SAE and will be reported as described in Sections 9.3.1 and 9.3.3:

- Spontaneous pregnancy loss, including:
 - spontaneous abortion, (spontaneous pregnancy loss before/at 22 weeks of gestation).
 - ectopic and molar pregnancy.
 - stillbirth (intrauterine death of foetus after 22 weeks of gestation).
- Any early neonatal death (i.e. death of a live born infant occurring within the first 7 days of life).
- Any congenital anomaly or birth defect (as per [CDC MACDP] guidelines) identified in the offspring of a study subject (either during pregnancy, at birth or later) regardless of whether the foetus is delivered dead or alive. This includes anomalies identified by prenatal ultrasound, amniocentesis or examination of the products of conception after elective or spontaneous abortion.

Furthermore, any SAE occurring as a result of a post-study pregnancy AND considered by the investigator to be reasonably related to the investigational vaccine(s)/product(s) will be reported to GSK Biologicals as described in Section 9.3.3. While the investigator is not obligated to actively seek this information from former study participants, he/she may learn of a pregnancy through spontaneous reporting.

9.2. Detecting and recording adverse events, serious adverse events and pregnancies**9.2.1. Time period for detecting and recording adverse events, serious adverse events and pregnancies**

All AEs starting within 30 days following administration of each dose of study vaccine/placebo must be recorded into the appropriate section of the eCRF, irrespective of intensity or whether or not they are considered vaccination-related.

The time period for collecting and recording SAEs will begin at the first receipt of study vaccine/placebo and will end 180 days following administration of the last dose of study vaccine/placebo for each subject. See Section [9.3](#) for instructions on reporting of SAEs.

All AEs/SAEs leading to withdrawal from the study will be collected and recorded from the time of the first receipt of study vaccine/placebo.

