9.4. Follow-up of adverse events, serious adverse events, and pregnancies

9.4.1. Follow-up of adverse events and serious adverse events

9.4.1.1. Follow-up during the study

After the initial AE/SAE report, the investigator is required to proactively follow each subject and provide additional relevant information on the subject's condition to GSK Biologicals (within 24 hours for SAEs; refer to [Table 25](#)).

All SAEs and pIMDs (serious or non-serious) documented at a previous visit/contact and designated as not recovered/not resolved or recovering/resolving will be reviewed at subsequent visits/contacts until the end of the study.

All AEs documented at a previous visit/contact and designated as not recovered/not resolved or recovering/resolving will be reviewed at subsequent visits/contacts until 30 days after the last vaccination.

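### The study-level respiratory holding rules count from any dose in the text but from dose 1 in Table 6, and ordinary non-serious AEs need be recorded for only 30 days after each dose

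*Protocol*

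**What the plan says.** **The rules.** The text of Protocol 6.4.5.4 has two study-level respiratory triggers. An ad hoc IDMC review follows "if 2 or more subjects experience related Grade 2 or higher respiratory AEs within 90 days after any dose". The hold reads: "Further enrolment and vaccination will be suspended if within 90 days after any study vaccine dose any of the following events are observed". The events listed under the hold are a related fatal respiratory AE, or related Grade 3 respiratory AEs in two or more subjects.

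Table 6, in the same section, restates these triggers. All three of its respiratory AE rows, two of them study-level, carry the label "Respiratory SOC AE (within 90 days after dose 1"). The fatal row has no window.

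Protocol 6.4.5.2 words the IDMC trigger differently. While enrolment and vaccination are under way, if "two or more related grade 2 or 3 respiratory AE are observed an ad hoc IDMC will be convened". It states no day count, and it counts events rather than subjects.

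**The data.** Protocol 9.2.1 requires recording of "All AEs starting within 30 days following administration of each dose of study" product. In Table 7 the row "Recording of unsolicited AEs and large swelling reactions" is marked from Visit 2 to Visit 6 (Month 2) and not at later contacts. Under 9.4.1.1, unresolved AEs "will be reviewed at subsequent visits/contacts until 30 days after the last vaccination".

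Some collection runs longer. SAEs are recorded to 180 days after the last dose, and related SAEs to study end. pIMDs are recorded to six months after dose 2. AEs leading to withdrawal are recorded from the first dose with no 30-day limit. For intercurrent conditions, 7.7 says "the condition(s) must be recorded in the eCRF", but it asks for neither an intensity grade nor a causality judgement.

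SAP 11.13 tabulates respiratory AEs by grade and relatedness over Day 0 to Day 89 in the total vaccinated cohort.

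**The concern.** A holding rule should give one answer for one set of facts. Here the text and the table of the same section can give two.

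The dose 1 anchor makes sense in the subject-level row, because that row decides whether the subject gets dose 2. It has no evident reason in the rows that trigger an action for the whole trial.

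The rule also depends on data that the protocol does not require for the whole window. Both study-level AE triggers need a grade and a causality assessment. An ordinary non-serious respiratory AE that starts more than 30 days after a dose, or that worsens to Grade 2 or 3 after review has ended, need not be captured with either. Solicited respiratory symptoms do not fill the gap: they cover seven days per dose in about 450 of 3506 subjects.

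At stake is a hold that is disputed, late or missed while people are still being vaccinated, and a 90-day safety table that may be less complete than its title suggests.

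**Working it through.** The plan gives no figure of its own here, so the check is a count of days.

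**Inputs**
- Interval between doses, g: 26 to 35 days (Protocol Table 8, Visit 2 to Visit 4).
- Text window: 90 days from each dose. Table 6 window: 90 days from dose 1 (6.4.5.4).
- Required AE recording: the dose day plus 29 days, after each dose (9.2.1 and the unsolicited AE endpoint in 11.2).
- Visit 4 to Visit 6: 26 to 35 days. Visit or contact to next contact: 6 to 12 weeks, or 42 to 84 days (Table 8).

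**Formulas for a two-dose subject**
- Days after dose 2 inside the Table 6 window = 90 − g.
- Length of text window = 90 + g.
- Days with required recording = 30 + min(g, 30).
- Days without it = window length minus recorded days.

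| | g = 26 | g = 30 | g = 35 |
|---|---|---|---|
| Post-dose-2 days inside Table 6 window | 64 | 60 | 55 |
| Post-dose-2 days dropped, of 90 | 26 (29%) | 30 (33%) | 35 (39%) |
| Text window, days | 116 | 120 | 125 |
| Days with required AE recording | 56 | 60 | 60 |
| Text window without recording | 60 (52%) | 60 (50%) | 65 (52%) |
| Table 6 window (90 days) without recording | 34 (38%) | 30 (33%) | 30 (33%) |

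A subject who receives dose 1 only has 90 − 30 = 60 unrecorded days under either version.

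Aligning Table 6 with the text therefore does not cure the recording gap, and keeping the Table 6 window would not close it either.

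**A worked case.** Take g = 30 and two subjects with related Grade 3 respiratory AEs on day 70 after dose 2, which is day 100 after dose 1. Under the text, 70 is less than 90, so enrolment and vaccination are suspended. Under Table 6, 100 is more than 90, so neither event counts.

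**Could existing contacts close the gap?**
- Month 4 contact, days after dose 2: 26 + 42 = 68 to 35 + 84 = 119.
- Next contact, if Month 4 falls on days 68 to 89: 68 + 42 = 110 to 89 + 84 = 173.
- Month 4 contact, days after dose 1, for a dose-1-only subject who keeps the schedule: 26 + 26 + 42 = 94 to 35 + 35 + 84 = 154.

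One contact, or two at most, reaches past day 90 in every case.

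**The case against.** **The windows are nested.** Ninety days from dose 1 lies inside 90 days from any dose, so a team that follows the text also satisfies Table 6, and nothing in the table cancels the text. This stands, and it makes the first part a drafting correction. The protocol does not, however, say which governs, and a reader working from the table would not hold.

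**The practical difference is narrow.** While enrolment and vaccination continue, 6.4.5.2 would still convene the IDMC, so only the automatic hold differs. Once vaccination is complete there is nothing left to suspend, and the IDMC still meets twice a year. This also stands. A reader might infer that after vaccination ends only the text calls for an ad hoc review. That is true only once the Table 6 window has closed, 55 to 64 days after dose 2.

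**Much is still captured.** A reader might infer that no non-serious AE is recorded after 30 days. The documents do not support that. Non-serious pIMDs are reported with causality, and the list includes sarcoidosis and idiopathic pulmonary fibrosis. AEs leading to withdrawal are recorded. Important medical events count as SAEs. TB-like respiratory symptoms prompt evaluation throughout. What remains uncovered is the ordinary non-serious Grade 2 or 3 event, which is what the two AE triggers count beyond SAEs.

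**Days are not events.** No event rate is given, so a window that is half unrecorded does not mean that half the triggers are lost. The eCRF, the study procedures manual and the IDMC charter cannot be seen here and might provide for longer collection. The SAP table therefore may under-count; it cannot be said that it will.

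**Conclusion.** The point holds in this form, and the change should be made. The text and Table 6 give different hold decisions when the related Grade 3 respiratory AEs needed to reach two subjects fall after the Table 6 window closes but within 90 days of dose 2. That stretch is 26 to 35 days per two-dose subject, and it matters while enrolment and vaccination are ongoing. Separately, ordinary non-serious AEs have no required recording with grade and causality on 60 to 65 days of the text window.

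The day counts assume dosing within the Table 8 interval and recording only as the protocol requires.

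A reader might also suspect a biased safety comparison. The recording rules are the same in both arms, so the documents give no ground for that: the risk is under-counting and a late or missed trigger. Alpha, power and the primary efficacy analysis are unaffected.

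**What to change.** 1. **Table 6.** Change the two study-level AE rows (related Grade 2 or higher, and related Grade 3 or higher, each in two or more subjects) to count from any dose. Leave the subject-level row as it is. Have 6.4.5.2 cross-refer to 6.4.5.4 without narrowing its own trigger, which is the broader one during enrolment and vaccination.
2. **Recording.** In 9.2.1, 9.4.1.1 and Table 7, extend recording of Grade 2 or higher respiratory AEs, with intensity and causality, to 90 days after the last dose received. Record them when the subject presents, and otherwise through a two-way question at the Month 4 contact, with the next contact added if Month 4 falls before day 90. A one-way SMS will not do.
3. **If recording is not extended,** footnote the 90-day table in SAP 11.13: *non-serious AEs collected for 30 days after each dose, except pIMDs (to 6 months post-dose 2) and AEs leading to withdrawal; SAEs collected throughout the 90 days.*

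The cost is wording in five places, one question and a little eCRF entry at one or two existing contacts, with no new visit or sample. The downside is some staff time, and that events not self-reported may surface weeks late: at a contact up to day 119 after dose 2, or day 173 if the next contact is needed. That is slow for a holding rule, so the instruction to report on presentation matters. The footnote alone costs almost nothing but leaves the trigger without its data.

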6.5. Outline of study procedures

Table 7 List of study procedures (Amended: 29 January 2014)

	Visit 1 Screening visit	Visit 2	Visit 3 ¹	Visit 4	Visit 5 ¹	Visit 6	Contact 1, 2, 3 and 4	Visit 7	Contact 5, 6, 7, 8, 9	Visit 8	Contact 10, 11, 12, 13, 14	Visit 9
Time point(s)	D-30 to D0	D 0	D 7	D 30	D 37	M 2	M 4, 6, 8, 10	M 12	M 14, 16, 18, 20, 22	M 24	M 26, 28, 30, 32, 34	M 36
Sampling Time point(s)	Pre V	Pre V	Post V1	Post V1	Post V2	Post V2	Post V2	Post V2	Post V2	Post V2	Post V2	Post V2
Dose		1		2								
All subjects												
Informed consent	•											
Check inclusion/exclusion criteria	•	•										
Collect demographic data	•											
Medical history	•	•										
Physical examination		•										
History-directed physical examination		0	0	0	0	0						
Resting vital signs		0		0								
HIV testing ² (up to ~ 2.5 mL/test)	•										•	
Record weight ³		•						•		•		•
Documentation of history of BCG vaccination/presence of scar	•										Visit 1	
Documentation of history of TB household contacts	•											
Pregnancy test (β-HCG urine)	•	•		•								
Study group and treatment number allocation for first dose		0										
Treatment number allocation for second dose				0								

CONFIDENTIAL

115616 (TUBERCULOSIS-018)
Protocol Amendment 5 Final

	Visit 1 Screening visit	Visit 2	Visit 3 ¹	Visit 4	Visit 5 ¹	Visit 6	Contact 1, 2, 3 and 4	Visit 7	Contact 5, 6, 7, 8, 9	Visit 8	Contact 10, 11, 12, 13, 14	Visit 9
Time point(s)	D-30 to D0	D 0	D 7	D 30	D 37	M 2	M 4, 6, 8, 10	M 12	M 14, 16, 18, 20, 22	M 24	M 26, 28, 30, 32, 34	M 36
Sampling Time point(s)	Pre V	Pre V	Post V1	Post V1	Post V2	Post V2	Post V2	Post V2	Post V2	Post V2	Post V2	Post V2
Dose		1		2								
Vaccination		●		●								
Recording of administered treatment number		●		●								
Check contraindications to subsequent vaccination		●		●								
Recording concomitant medication/vaccination		●	●	●	●	●	●	●	●	●	●	●
Recording intercurrent medical condition		●	●	●	●	●	●	●	●	●	●	●
Distribution of diary cards		0		0								
Return of diary cards				0		0						
Recording of unsolicited AEs and large swelling reactions		●	●	●	●	●						
Pre-vaccination assessment (including temperature)		●		●								
Blood sampling for QFTG (~ 3 mL)	●											
Sputum collection for Xpert testing	●											
Reporting SAEs	● ⁴	●	●	●	●	●	● ⁵	● ⁴	● ⁴	● ⁴	● ⁴	● ⁴
Reporting pIMDs	●	●	●	●	●	●	● ⁶					
Reporting pregnancy	●	●	●	●	●	●	● ⁶					
Diagnostic procedures for suspected pulmonary TB ⁷			●	●	●	●	●	●	●	●	●	●
Documentation of TB cases ⁸			●	●	●	●	●	●	●	●	●	●

CONFIDENTIAL

115616 (TUBERCULOSIS-018)
Protocol Amendment 5 Final

	Visit 1 Screening visit	Visit 2	Visit 3 ¹	Visit 4	Visit 5 ¹	Visit 6	Contact 1, 2, 3 and 4	Visit 7	Contact 5, 6, 7, 8, 9	Visit 8	Contact 10, 11, 12, 13, 14	Visit 9
Time point(s)	D-30 to D0	D 0	D 7	D 30	D 37	M 2	M 4, 6, 8, 10	M 12	M 14, 16, 18, 20, 22	M 24	M 26, 28, 30, 32, 34	M 36
Sampling Time point(s)	Pre V	Pre V	Post V1	Post V1	Post V2	Post V2	Post V2	Post V2	Post V2	Post V2	Post V2	Post V2
Dose		1		2								
Safety and immune sub-cohort												
Measuring Vitamin D		●										
Recording of solicited AEs		●	●	●	●							
CBC (Hb, PLT and WBC), ALT, AST, creatinine, bilirubin (~ 8 mL)		●	●	●	●							
Blood sampling for Wh.BI. CMI (~ 2.5 mL)		●				●		●		●		●
Blood sampling for humoral immunogenicity (~ 2 mL)		●				●		●		●		●
Study conclusions for all subjects												●

Note: The double border at Month 36 indicates the final analyses which will be performed on all data obtained up to month 36.

Pre V: Pre Vaccination; V: Vaccination; Post V: Post Vaccination

● is used to indicate a study procedure that requires documentation in the individual eCRF.

○ is used to indicate a study procedure that does not require documentation in the individual eCRF.

1 Only subjects in the safety and immune sub-cohort need to come for this visit.

2 HIV testing, pre-test **and post-test** counselling will be performed **whenever a HIV test is done**, according to the procedures detailed in [Table 10](#).

3 Weight also needs to be recorded whenever there is suspicion of TB disease.

4 Only SAEs related to study participation or concurrent GSK medication/vaccine.

5 SAEs not related to study participation or concurrent GSK medication/vaccines will be recorded until 6 months post dose 2 (M7).

6 To be recorded until 6 months post dose 2 (M7).

7 Sputum samples for Xpert MTB/RIF testing and microbiological culture will be taken throughout the study if a subject presents with clinical suspicion of pulmonary TB disease. Three sputum samples, preferably taken in the morning and within **max.** one week, must be collected. Additionally, when a subject is diagnosed with TB, **screening for diabetes (HbA1C)** **and** HIV testing must be performed according to the procedures detailed in [Table 10](#). Up to 2.5mL of blood will be collected per test. If the subject is confirmed HIV-positive, blood samples must be taken (2.5 mL) to measure CD4 counts.

8 Documentation of TB cases will be done throughout the study, starting at Visit 3 (Day 7); this includes documentation of cases during active and passive follow-up and monitoring of medical facilities and pharmacies.

Table 8 Intervals between study visits for all subjects (Amended: 29 January 2014)

Interval	Allowed interval ¹
Visit 1 - Visit 2	0 days - 30 days
Visit 2 - Visit 4	26 days - 35 days
Visit 4 - Visit 6	26 days - 35 days
Visit 4 - Visit 7	10 months - 12 months
Visit 4 - Visit 8	22 months - 24 months
Visit 4 - Visit 9	34 months - 36 months
Visit n - next contact	6 weeks - 12 weeks
Contact n - contact n+1	6 weeks - 12 weeks

¹ Subjects may not be eligible for inclusion in the ATP cohort for analysis of immunogenicity and efficacy if they **attend for a** study visit outside this interval.

Table 9 Intervals between study visits specific for the safety and immune sub-cohort

Interval	Allowed interval ¹
Visit 2 - Visit 3	6 days - 10 days
Visit 4 - Visit 5	6 days - 10 days

¹ Subjects may not be eligible for inclusion in the ATP cohort for analysis of immunogenicity and efficacy if they make the study visit outside this interval.

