3. STUDY DESIGN OVERVIEW

Figure 2 Overview of the study design (Amended: 29 January 2014)

Protocol waivers or exemptions are not allowed with the exception of immediate safety concerns. Therefore, adherence to the study design requirements, including those specified in the outline of study procedures (Section 6.5), are essential and required for study conduct.

- **Experimental design:** Phase IIb, randomised, double-blind, controlled, multi-centre, efficacy study with two parallel groups.
- **Duration of the study:** the duration of the study will be approximately 37 months for each subject from screening up to end of efficacy follow-up.
 - Epoch 001: Primary starting visit 1 (screening visit) and ending visit 10 (Month 36).
- **Study groups:** Study groups and treatments foreseen in the study are presented in [Table 1](#) and [Table 2](#).

Table 1 Study groups and epochs foreseen in the study (Amended: 29 January 2014)

Study Groups	Number of subjects	Age (Min - Max) (age unit)	Epoch 001
M72AS01	1753	18 years - 50 years	x
Control	1753	18 years - 50 years	x

Table 2 Study groups and treatment foreseen in the study

Treatment name	Vaccine/Product name	Study Groups	
		M72AS01	Control
M72/AS01 _E	M72	x	
	AS01 _E	x	
Placebo	Placebo pellet		x
	Placebo adjuvant		x

- **Control:** placebo control.
- **Vaccination schedule:** Subjects will receive 2 doses of M72/AS01_E or placebo, according to their random assignment, one month apart (Day 0 and Day 30) by intramuscular injection in the deltoid region of the arm.
- **Treatment allocation:** Randomised 1:1. Randomisation will occur at the day of first vaccination (Day 0). Refer to Section 6.2 for a detailed description of the randomisation method.
- **Blinding:** Double-blind (Table 3). Refer to Section 6.3 for method of blinding.

Table 3 Blinding of study epochs

Study Epochs	Blinding
Epoch 001	double-blind

- **Sampling schedule (Amended: 29 January 2014):**
 - Blood samples will be collected in the safety and immune sub-cohort for evaluation of biochemistry/haematology parameters (Days 0, 7, 30 and 37), CMI responses (Days 0, 60 and Years 1, 2 and 3) and humoral immune responses (Days 0, 60 and Years 1, 2 and 3). **Vitamin D levels will be measured at Day 0.**
 - Blood samples will be collected for QFTG testing at **screening** for all subjects.
 - **A respiratory sputum sample will be collected prior to vaccination in all subjects for nucleic acid amplification test to rule out pulmonary TB.**

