SAEs that are related to the investigational vaccine/product will be collected and recorded from the time of the first receipt of study vaccine/placebo until the subject is discharged from the study.

In addition to the above-mentioned reporting requirements and in order to fulfil international reporting obligations, SAEs that are related to study participation (i.e. protocol-mandated procedures, invasive tests, a change from existing therapy) or are related to a concurrent GSK medication/vaccine will be collected and recorded from the time the subject consents to participate in the study until she/he is discharged from the study.

The time period for collecting and recording pregnancies will begin at the first receipt of study vaccine/placebo and will end 180 days following administration of the last dose of study vaccine/placebo. See section [9.3](#) for instructions on reporting of pregnancies.

The time period for collecting and recording of pIMDs will begin at the first receipt of study vaccine/placebo and will end 180 following administration of the last dose of study vaccine/placebo. See section [9.3](#) for instructions on reporting of pIMDs.

An overview of the protocol-required reporting periods for AEs, SAEs, and pregnancies is given in [Table 23](#).

Table 23 Reporting periods for adverse events, serious adverse events and pregnancies

Study activity	Pre-vacc*	Dose 1 (V1) D 0	7 d post V1 D 6	30 d post V1 D 29	Dose 2 (V2) D 30	7 d post V2 D 36	30 d post V2 D 59	6 months post dose 2 M 7	Study Conclusion M36
Reporting of solicited AEs [†]									
Reporting of unsolicited AEs									
Reporting of SAEs									
Reporting of SAEs related to the investigational product									
Reporting of SAEs related to study participation or concurrent GSK medication/vaccine									
Reporting of pregnancies									
Reporting of pIMDs									

* i.e. consent obtained.

Pre-Vacc: pre-vaccination; V: vaccination; Post-V: post-vaccination; D: Day, M: Month

[†] For the safety and immune sub-cohort only

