11.14. Serious adverse events

Percentage of subjects reporting the occurrence of SAEs classified by MedDRA Primary S O C and P T will be tabulated with exact 95% CI by treatment group.

The same tabulations will be done for SAEs with causal relationship to vaccination and for fatal SAEs.

As reporting periods for AE, SAEs and related SAE differ, these tabulations will be done for events occurring during the 30-Day (Days 0-29) post vaccination, during the period from Day 0 to Month 7 and during the entire study period as indicated in the following table.

	Post vaccination period considered		
	30-day post-vaccination period	From Day 0 to Month 7	From Day 0 to end of study*
SAEs	X	X	X**
Related-SAE(s)	X	X	X
Fatal SAE(s)			X

* For the triggered primary analysis: it will be from day 0 to database freeze

** performed only for the CTR tables

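### Table 7 footnotes 4 and 5 leave out SAEs related to the study vaccine after Month 7, although section 9.2.1 requires them until discharge

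*Protocol*

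**What the plan says.** **Table 7 (protocol section 6.5).** The row "Reporting SAEs" has no footnote at Visits 2 to 6. It carries footnote 5 at Contacts 1 to 4 (Months 4, 6, 8 and 10). It carries footnote 4 at Visit 1, at Visits 7 to 9 (Months 12, 24 and 36) and at Contacts 5 to 14.

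- Footnote 4: "Only SAEs related to study participation or concurrent GSK medication/vaccine".
- Footnote 5: "SAEs not related to study participation or concurrent GSK medication/vaccines will be recorded until 6 months post dose 2 (M7".

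**Section 9.2.1** sets these collection periods:

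- All SAEs: from first dose, in a period that "will end 180 days following administration of the last dose of study vaccine/placebo for each subject".
- Vaccine-related SAEs: "SAEs that are related to the investigational vaccine/product will be collected and recorded from the time of the first receipt", and on until the subject is discharged from the study.
- As a further requirement, from consent until discharge: SAEs "related to study participation (i.e. protocol-mandated procedures, invasive tests, a change from existing therapy"), or related to a concurrent GSK product.
- AEs and SAEs leading to withdrawal from the study: from first dose, with no end date given.

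Table 23 gives SAEs related to the investigational product their own row, separate from the row for study participation and concurrent GSK products.

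**SAP 11.14** first describes tables of all SAEs and then adds: "The same tabulations will be done for SAEs with causal relationship to vaccination and for fatal SAEs". Its grid marks related SAEs for 30 days, for Day 0 to Month 7, and for Day 0 to end of study.

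**The concern.** A site that follows the schedule literally is told, from Month 12 on, to report two classes of SAE and no others. The study vaccine belongs to neither class. The word only in footnote 4 excludes events, so a reader has no cue that something is missing and should be looked up elsewhere. Section 3 adds weight to the schedule by saying that "adherence to the study design requirements, including those specified in the outline of study procedures (Section 6.5), are essential and required".

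What is at stake is the completeness of late vaccine-related SAE reports. If some sites work from Table 7 and others from section 9.2.1, the end-of-study table of related SAEs will have uneven capture after Month 7. Nothing in that table would separate an event that did not occur from one that was not recorded.

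**Working it through.** No power, sample-size or event-count figure is involved. The check is a comparison of the texts plus a count of schedule points.

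**1. Does the general cut-off agree?** Dose 2 is at Day 30. Day 30 + 180 days = Day 210, which is 7 months of 30 days. Footnote 5's Month 7 therefore matches section 9.2.1 for SAEs in general, and there is no conflict on that class.

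**2. Class by class after Month 7.**

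| Class | Section 9.2.1 | Table 7 after Month 7 | Agree? |
|---|---|---|---|
| SAEs in general | ends 180 days after last dose | ended by footnote 5 | yes |
| Related to study participation or a concurrent GSK product | consent to discharge | listed in footnote 4, exempt from footnote 5 | yes |
| Related to the study vaccine | first dose to discharge | not listed in footnote 4, ended by footnote 5 | no |
| AE/SAE leading to withdrawal | from first dose, no end stated | not listed | no |

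**3. Could the footnotes be read to include the study vaccine?**

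- Study participation: section 9.2.1 explains the term as procedures, invasive tests and a change of therapy. Vaccination effects are not among them.
- Concurrent GSK medication or vaccine: section 9.2.1 introduces this class in addition to the vaccine-related class, and Table 23 puts the two in separate rows.

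Neither reading works.

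**4. A clue in the schedule.** Footnote 4 is also attached to Visit 1. Before any dose there can be no vaccine-related SAE, so its wording is correct there. The same wording reappears after vaccination, where it no longer fits.

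**5. Extent.**

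- Scheduled points after Month 2: 14 contacts + 3 visits = 17.
- Points before Month 7: Contacts 1 and 2 (Months 4 and 6) = 2.
- Points after Month 7: Contacts 3 to 14 (12) + Visits 7 to 9 (3) = 15. Of these, 13 fall under footnote 4, and 2 (Months 8 and 10) under footnote 5.
- Time: 36 − 7 = 29 months; 29/36 = 81% of the schedule from Day 0.
- Subjects: the row applies to all subjects, about 3506.

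The period bars in Table 23 are not legible in the copy reviewed, so only its row structure is used here.

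**The case against.** The best defence is that Table 7 is an outline and the operative rules lie elsewhere. The recording instructions at section 6.6.15 send the investigator to section 9.2. Section 9.3.1 ties prompt reporting to the periods in section 9.2.1. Table 23 has a row for the vaccine-related class. Section 9.2.2 asks for prompt notification of a vaccine-related SAE learned of even after discharge. Section 3 makes the schedule binding but does not rank it above section 9. All of this stands. A reader might infer that vaccine-related SAEs after Month 7 will go uncollected, or will not reach the sponsor or the IDMC. The documents do not support that, because a site that follows section 9 will report them.

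Three further inferences also go too far:

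- *That related SAEs are the only long-term safety read-out.* SAP 11.14 also tabulates fatal SAEs to end of study, and all SAEs over that period for the CTR tables. Unresolved SAEs and pIMDs are reviewed until the end of the study (section 9.4.1.1).
- *That this is the only class meant to run to discharge.* SAEs related to study participation or a concurrent GSK product do so too, and Table 7 keeps them.
- *That the end-of-study table would show zero events.* It starts at Day 0 and would still hold related SAEs recorded up to Month 7.

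The defence does not remove the contradiction. Cross-references to section 9 do not cancel an instruction that says only, in a schedule that section 3 calls required.

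**Conclusion.** The contradiction is real and stands in the current Amendment 5 text. Section 9.2.1 sets a sound rule and SAP 11.14 relies on it; Table 7 departs from it. The consequence is a risk of under-collecting late vaccine-related SAEs, from about Month 7 to Month 36, at 15 of the 17 scheduled points after Month 2.

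How many events could be missed cannot be worked out from the documents. It depends on how many sites work from Table 7 without consulting section 9, and on how many vaccine-related SAEs arise that late; neither is stated. The conclusion rests on two readings: that study participation has the meaning section 9.2.1 gives it, and that a concurrent GSK product is something other than the study vaccine. This is an inconsistency between a schedule and the section that governs it, and does not call the design itself into question. It should be corrected because the correction is simple and the class concerned is late vaccine safety.

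**What to change.** Reconcile Table 7 with section 9.2.1 and Table 23:

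1. Keep the present footnote 4 at Visit 1 only. Adding the study vaccine to it in place would list vaccine-related SAEs at a visit before any dose, whereas section 9.2.1 starts that class at first dose.
2. Attach a new footnote to Visits 7 to 9 and Contacts 5 to 14 that admits SAEs related to the investigational vaccine/product, to study participation or to a concurrent GSK medication/vaccine, and AEs/SAEs leading to withdrawal.
3. Amend footnote 5 so that the Month 7 limit does not apply to any of those classes. This covers the Month 8 and Month 10 contacts.
4. Remind sites that section 9.2.1 governs the reporting periods.

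Adding only the study vaccine to the footnotes would still leave AEs/SAEs leading to withdrawal out of line with section 9.2.1, which is why step 2 names them.

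The cost is a short footnote change in a protocol amendment and a note to sites. No visit, contact or procedure is added, and SAP 11.14 needs no change.
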